***Definition:**

- *for subjects with a pre-vaccination anti-RV IgA antibody concentration <20 U/mL, seroconversion is achieved when the post-vaccination concentration is ≥ 20 U/mL.*
- *for subjects with a pre-vaccination anti-RV IgA antibody concentration ≥ 20 U/mL, seroconversion is achieved when the post-vaccination concentration is ≥ 2 times the pre-vaccination concentration.*
- Solicited general symptoms
 - Occurrence of each type of solicited general symptom within the 8-day (Day1-Day 8) solicited follow-up period, after each dose of HRV lyophilized vaccine and HRV liquid vaccine.
- Unsolicited adverse events
 - Occurrence of unsolicited AEs within 31 days (Day 1- Day 31) after any dose of HRV lyophilized vaccine and HRV liquid vaccine according to Medical Dictionary for Regulatory Activities (MedDRA) classification.

- Serious adverse events
 - Occurrence of SAEs from dose 1 of HRV lyophilized vaccine and HRV liquid vaccine up to study end.

TABLE OF CONTENTS

	PAGE
SPONSOR INFORMATION	7
SYNOPSIS.....	8
LIST OF ABBREVIATIONS	19
GLOSSARY OF TERMS	21
TRADEMARK.....	25
1. INTRODUCTION.....	26
1.1. Background (Amended: 30 October 2019).....	26
1.2. Rationale for the study and study design	26
1.3. Benefit: Risk Assessment	27
1.3.1. Risk Assessment	27
1.3.2. Benefit Assessment	28
1.3.3. Overall Benefit: Risk Conclusion	28
2. OBJECTIVES.....	28
2.1. Primary objective	28
2.2. Secondary objectives (Amended: 30 October 2019).....	28
3. STUDY DESIGN OVERVIEW	29
4. STUDY COHORT.....	31
4.1. Number of subjects/centers	31
4.2. Inclusion criteria for enrolment	31
4.3. Exclusion criteria for enrolment.....	31
5. CONDUCT OF THE STUDY	33
5.1. Regulatory and ethical considerations, including the informed consent process.....	33
5.2. Subject identification and randomization	34
5.2.1. Subject identification	34
5.2.2. Randomization of treatment	34
5.2.2.1. Randomization of supplies.....	34
5.2.2.2. Treatment allocation to the subject	34
5.2.2.2.1. Study group and treatment number allocation	34
5.2.2.2.2. Treatment number allocation for subsequent doses	35
5.3. Method of blinding	35
5.4. General study aspects	35
5.5. Outline of study procedures	35
5.6. Detailed description of study procedures	37
5.6.1. Informed consent	37
5.6.2. Check inclusion and exclusion criteria	37
5.6.3. Collect demographic data	37
5.6.4. Medical and vaccination history	37

- 5.6.5. Physical examination 37
- 5.6.6. Check contraindications, warnings and precautions to vaccination..... 38

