***Definition:**

- *for subjects with a pre-vaccination anti-RV IgA antibody concentration <20 U/mL, seroconversion is achieved when the post-vaccination concentration is ≥ 20 U/mL.*
- *for subjects with a pre-vaccination anti-RV IgA antibody concentration ≥ 20 U/mL, seroconversion is achieved when the post-vaccination concentration is ≥ 2 times the pre-vaccination concentration.*
- To assess the reactogenicity of the HRV liquid vaccine and the HRV lyophilized vaccine in terms of solicited adverse events (AEs), during the 8-day (Day 1–Day 8) follow-up period after each vaccination.

- To assess the safety of the HRV liquid vaccine and the HRV lyophilized vaccine in terms of unsolicited AEs, during the 31-day (Day 1–Day 31) follow-up period after each vaccination and serious adverse events (SAEs), during the entire study period.

Refer to Section 10.2 for the definition of the secondary endpoints.

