3. STUDY DESIGN OVERVIEW

N= number of subjects planned to be enrolled; HRV= Human Rotavirus; Pre-Vacc= Pre-vaccination; Post-Vacc=Post-Vaccination; BS=Blood sample

Protocol waivers or exemptions are not allowed unless necessary for the management of immediate safety concerns. Therefore, adherence to the study design requirements, including those specified in the outline of study procedures (Section 5.5), are essential and required for study conduct.

- Experimental design:** Phase III, open-label, randomized (1:1), multi-centric, single-country study with two parallel groups.
- Duration of the study:** The intended duration of the study, per subject, is approximately two months.
 - Epoch 001: Primary starting at Visit 1 (Day 1) and ending at Visit 3 (Month 2).
- Primary Completion Date (PCD):** Last subject attending Visit 3.

Refer to [glossary of terms](#) for the definition of PCD.

- End of Study (EoS):** Last testing results released for samples collected at Visit 3.

Refer to [glossary of terms](#) for the definition of EoS.

- Study groups:** The study groups and epoch foreseen in the study are provided in [Table 1](#).

Table 1 Study groups and epoch foreseen in the study

Study groups	Number of subjects	Age at Dose 1 (Min/Max)	Epoch 001
HRV Liq	225	6 weeks-10 weeks	●
HRV Lyo	225	6 weeks- 10 weeks	●

- **Treatment groups:** Table 2 presents the study groups and the vaccine to be administered in the study.
 - HRV Liquid vaccine group (also referred to as HRV Liq)
 - HRV Lyophilized vaccine group (also referred to as HRV Lyo).

Table 2 Study groups and treatment foreseen in the study

Treatment name	Vaccine/Product name	Study Groups	
		HRV Liq	HRV Lyo
HRV Liquid	GSK Biologicals' HRV liquid vaccine	x	
HRV Lyophilized	GSK Biologicals' HRV lyophilized vaccine		x
	GSK Biologicals' calcium carbonate buffer		x

- **Control:** active control (Lyophilized HRV vaccine)
- **Vaccination schedule:**
 - Two oral doses of the HRV vaccine to be given according to a 0, 1 month schedule.
 - All subjects are allowed to receive routine childhood vaccinations according to the local immunization practice. Administration of all routine childhood vaccinations given since birth will be recorded in the electronic Case Report Form (eCRF).
- **Treatment allocation:** Randomized (1:1). Treatment number will be allocated using GSK Biologicals' Randomization System on Internet (SBIR).
- **Blinding:** open

The blinding of study epoch is provided in Table 3.

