5.5. Outline of study procedures

The list of study procedures is detailed in [Table 4](#).

Table 4 List of study procedures

Age at enrolment	6-10 weeks		
Epoch	Epoch 001		
Type of contact	Visit 1	Visit 2	Visit 3
Time points	Day 1	Month 1	Month 2
Sampling time points	Pre-Vacc		Post-Vacc
Informed consent	●		
Check inclusion/exclusion criteria	●		
Collect demographic data	●		
Check contraindications and warnings and precautions	●	●	
Medical history	●		
Physical examination	●		
History of previous vaccination from birth	●		
Pre-vaccination body temperature	●	●	
Vaccines			
Study group and treatment number allocation	○		
Treatment number allocation for subsequent doses		○	
Recording of administered treatment number	●	●	
HRV vaccine administration	●	●	
Record regurgitation	●	●	
HRV vaccine replacement dose administration in case of regurgitation *	●	●	
Laboratory Assays			
Blood sampling for antibody determination (~2 ml)	●		●
Safety assessments			
Distribution of diary cards	○	○	
Recording of solicited adverse events within 8 days after each dose of HRV vaccine (Day 1–Day 8)	●	●	
Recording of non-serious adverse events within 31 days (Day 1–Day 31) post-vaccination	●	●	●
Record any concomitant medication/vaccination	●	●	●
Record any intercurrent medical conditions	●	●	●
Recording of AEs/SAEs leading to withdrawal from study	●	●	●
Recording of SAEs	●	●	●
Recording of SAEs related to study participation, or to a concurrent GSK medication/vaccine	●	●	●
Return of diary cards		○	○
Diary card transcription by investigator		●	●
Study Conclusion			●

● is used to indicate a study procedure that requires documentation in the individual eCRF.

○ is used to indicate a study procedure that does not require documentation in the individual eCRF.

LAR = Legally Acceptable Representative; AE = Adverse Events; SAE = Serious Adverse Events

* If regurgitation or vomiting occurs after vaccination, a single replacement dose may be given at the same vaccination visit at the discretion of the Investigator.

Note: All subjects are allowed to receive routine childhood vaccinations according to the local immunization practice.

Whenever possible the investigator should arrange the study visits within the interval provided in [Table 5](#).

Table 5 Intervals between study visits

Interval	Optimal length of interval ¹	Allowed interval
Visit 1 → Visit 2	1 month	28-48 days after Dose 1
Visit 2 → Visit 3	1 month	31-48 days after Dose 2

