¹ Whenever possible the investigator should arrange the study visits within this interval.

Note: The date of the previous visit serves as the reference date for the intervals between the study visits.

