8.2. Detecting and recording adverse events and serious adverse events

8.2.1. Time period for detecting and recording adverse events and serious adverse events

All AEs starting within 31 days following administration of each dose of study vaccines (Day 1 to Day 31) must be recorded into the appropriate section of the eCRF, irrespective of intensity or whether or not they are considered vaccination-related.

The time period for collecting and recording SAEs will begin at the receipt of study vaccine and will end 30 days following administration of the last dose of study vaccine for each subject. See Section 8.3 for instructions on reporting of SAEs.

All AEs/SAEs leading to withdrawal from the study will be collected and recorded from the time of the first receipt of study vaccines.

In addition to the above-mentioned reporting requirements and in order to fulfil international reporting obligations, SAEs that are related to study participation (i.e., protocol-mandated procedures, invasive tests, a change from existing therapy) or are related to a concurrent GSK medication/vaccine will be collected and recorded from the time the subject consents to participate in the study until she/he is discharged from the study.

An overview of the protocol-required reporting periods for AEs and SAEs is given in [Table 12](#).

Table 12 Reporting periods for collecting safety information

Event	Pre-V1*	V1	7 days post vacc	30 days post vacc		V2	7 days post vacc	30 days post vacc		V3
		D1	D 8	D 31		M1				M2
										Study Conclusion
Solicited general AEs										
Unsolicited AEs										
AEs/SAEs leading to withdrawal from the study										
SAEs										
SAEs related to study participation or concurrent GSK medication/vaccine										

* Consent obtained. Pre-V: pre-vaccination; Post-Vacc: post-vaccination; V: Visit; D: Day, M: Month; AEs = Adverse Events; SAEs = Serious Adverse Events

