****Definition:***

- ***for subjects with a pre-vaccination anti-RV IgA antibody concentration <20 U/mL, seroconversion is achieved when the post-vaccination concentration is ≥20 U/mL.***

- **for subjects with a pre-vaccination anti-RV IgA antibody concentration ≥ 20 U/mL, seroconversion is achieved when the post-vaccination concentration is ≥ 2 times the pre-vaccination concentration.**
- Solicited general symptoms
 - Occurrence of each type of solicited general symptom within the 8-day (Day1-Day 8) solicited follow-up period, after each dose of HRV vaccine.
- Unsolicited adverse events
 - Occurrence of unsolicited AEs within 31 days (Day 1-Day 31) after any dose of HRV vaccine according to Medical Dictionary for Regulatory Activities (MedDRA) classification.
- Serious adverse events
 - Occurrence of SAEs from dose 1 of HRV vaccine up to study end.

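### Protocol 8.2.1 stops general SAE collection 30 days after the last dose, but the SAE objective and endpoint run to study end, 1 to 18 days later for every Visit 3 inside its window

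*Protocol*

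**What the plan says.** **Collection rule.** Protocol 8.2.1 starts general SAE collection at receipt of study vaccine and says that it "will end 30 days following administration of the last dose of study vaccine for each subject".

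**Objective.** Protocol 2.2 (also the synopsis and SAP 3.2) sets out to assess "serious adverse events (SAEs), during the entire study period".

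**Endpoint.** Protocol 10.2 and SAP 4.2 define it as "Occurrence of SAEs from dose 1 of HRV vaccine up to study end". The synopsis has "Occurrence of SAEs from dose 1 of HRV lyophilized vaccine and HRV liquid vaccine up to study end".

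**End of the subject's participation.** Protocol section 3 ends the single epoch at Visit 3. Table 5 in protocol 5.5, and Table 4 in SAP section 2, allow Visit 3 "31-48 days after Dose 2". The optimal interval is 1 month, with the footnote "Whenever possible the investigator should arrange the study visits within this interval".

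**Wider rules for some SAEs.** In 8.2.1, SAEs tied to study participation or to a concurrent GSK product "will be collected and recorded from the time the subject consents to participate in the study until she/he is discharged from the study". AEs and SAEs that lead to withdrawal are collected from the first vaccination, with no end date given.

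**The concern.** The endpoint needs data up to study end, while the collection rule closes earlier. Take a new SAE that starts after day 30 but before Visit 3, does not cause withdrawal, and is not linked to study participation or a concurrent GSK product. The 8.2.1 sentence does not ask the site to record it. The cut-off also matters operationally, because protocol 8.3.1 attaches prompt reporting to SAEs occurring in the period set by section 8.2.

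Sites could reasonably apply different periods. The SAP does not settle the matter: section 6.4.1.1 promises a description of SAEs in the study period without giving a window. A reader of the study report could not tell whether the days just before Visit 3 were covered. What is at stake is the completeness of a named secondary safety endpoint, which protocol 10.9 treats as descriptive.

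**Working it through.** **Inputs**

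- End of general SAE collection: 30 days after the last dose (protocol 8.2.1).
- Visit 2: 28 to 48 days after dose 1; Visit 3: 31 to 48 days after dose 2 (protocol Table 5).
- Study end for a subject: Visit 3 (protocol section 3). This is the reading that gives the smaller gap. The formal End of Study, release of the last Visit 3 test results, is later.

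**The plan's own day label.** With vaccination on Day 1, 30 days later is Day 1 + 30 = Day 31. This matches the heading of Table 12, which labels 30 days post-vaccination as D 31.

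**Gap for a two-dose subject** = (days from dose 2 to Visit 3) − 30

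- Earliest allowed Visit 3: 31 − 30 = 1 day, the visit day itself.
- Latest allowed Visit 3: 48 − 30 = 18 days.
- Every value from 31 to 48 exceeds 30, so no in-window Visit 3 falls on or before the cut-off.

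**Gap as a share of the time from dose 1 to Visit 3**

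| Case | Calculation | Share |
|---|---|---|
| Both visits at 31 days | 1/(31 + 31) = 1/62 | 1.6% |
| Smallest inside the windows | 1/(48 + 31) = 1/79 | 1.3% |
| Largest inside the windows | 18/(28 + 48) = 18/76 | 23.7% |

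**One-dose subjects.** Protocol 6.5 and 9.2.2 let a subject stop vaccination but stay in the study. The documents give no visit schedule for them. Assuming they keep the Table 5 intervals, Visit 3 falls 28 + 31 = 59 to 48 + 48 = 96 days after dose 1, and the gap is 59 − 30 = 29 to 96 − 30 = 66 days.

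**Sensitivity to day counting.** Section 8.2.1 also describes its 31-day AE period as Day 1 to Day 31. If the 31 to 48 of Table 5 were day numbers of that kind, elapsed time would be 30 to 47 days and the gap 0 to 17 days. Table 5 counts days after dose 2 and takes the previous visit's date as reference, which supports 1 to 18.

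**The case against.** The strongest reply is that sites would in practice record these events. Table 4 lists SAE recording at Visit 3. Section 8.2.3.1 has parents asked about changes since the last visit. Section 1.3.1 promises safety follow-up to the end of the study and immediate reporting of SAEs. Section 8.3.3 requires a report within 24 hours of learning of any SAE in a study subject. This stands as a limit on how many events would be lost, but a tick saying when to record does not override an explicit period, and 1.3.1 is itself at odds with the 8.2.1 sentence.

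A second reply is that section 8.2.2 defines post-study events by Table 12, so that table controls. Its bars could not be read in the text available here, and the SAE row must be checked. The row cannot remove the conflict: if the bar stops at 30 days it contradicts the endpoint, and if it reaches Visit 3 it contradicts the sentence it summarises.

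Third, the size rests on the edges of the windows. That is fair. Near the visit target the gap is only the visit day, and the largest share needs the earliest Visit 2 with the latest Visit 3. One per-protocol criterion (protocol 10.4.2) also accepts samples from 21 days after dose 2. A visit at 21 to 30 days would leave no gap, but Table 5 does not allow one.

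**Conclusion.** The concern holds. Current text sets two SAE periods that cannot both be followed, and high confidence attaches to that mismatch. The size of 1 to 18 days per two-dose subject rests on elapsed-day counting, on Visit 3 as study end, and on visits kept within Table 5. The one-dose range is conditional on a schedule that the documents do not state. How many subjects are affected, and how many SAEs might be missed, cannot be worked out, because actual visit dates are not given. No effect on the primary non-inferiority analysis, power or the comparison between arms is claimed. The passages should be reconciled, but this is not a threat to the trial's main conclusion.

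**What to change.** State one SAE period and use it everywhere. There are two ways:

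- **(a) Extend collection.** Change the 8.2.1 sentence so that all SAEs are recorded from dose 1 through the subject's Visit 3, and correct the SAE row of Table 12 if needed. Say that this includes one-dose subjects, and which contact ends collection for them. This keeps the stated objective and uses a visit at which SAE recording is already planned.
- **(b) Narrow the endpoint.** Restate the SAE objective and endpoint as ending 30 days after the last dose, in the protocol synopsis, 2.2 and 10.2 and in SAP 3.2 and 4.2.

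Option (a) is preferable because it preserves the objective. Under either option, SAP 6.4.1.1 should name the window that its SAE description covers.

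The cost is a few lines of text, no added visit, and a protocol amendment with ethics committee review (protocol 5.1). Option (a) may not reach subjects who have already finished; at least 141 were enrolled before Amendment 4. The study report should therefore say which SAE period was actually applied.

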8.2.2. Post-Study adverse events and serious adverse events

A post-study AE/SAE is defined as any event that occurs outside of the AE/SAE reporting period defined in Table 12. Investigators are not obligated to actively seek AEs or SAEs in former study participants. However, if the investigator learns of any SAE at any time after a subject has been discharged from the study, and he/she considers the event reasonably related to the study vaccines, the investigator will promptly notify the Study Contact for Reporting SAEs.

8.2.3. Evaluation of adverse events and serious adverse events

8.2.3.1. Active questioning to detect adverse events and serious adverse events

As a consistent method of collecting AEs, the subject’s parent(s)/LAR(s) should be asked a non-leading question such as:

‘Has your child acted differently or felt different in any way since receiving the vaccines or since the last visit?’

When an AE/SAE occurs, it is the responsibility of the investigator to review all documentation (e.g., hospital progress notes, laboratory and diagnostics reports) relative to the event. The investigator will then record all relevant information regarding an AE/SAE in the eCRF. The investigator is not allowed to send photocopies of the subject's medical records to GSK Biologicals instead of appropriately completing the eCRF. However, there may be instances when copies of medical records for certain cases are requested by GSK Biologicals. In this instance, all subject identifiers will be blinded on the copies of the medical records prior to submission to GSK Biologicals.

The investigator will attempt to establish a diagnosis pertaining to the event based on signs, symptoms, and/or other clinical information. In such cases, the diagnosis should be documented as the AE/SAE and not the individual signs/symptoms.

8.2.3.2. Assessment of adverse events

8.2.3.2.1. Assessment of intensity

The intensity of the following solicited AEs will be assessed as described in [Table 13](#):

Table 13 Intensity scales for solicited symptoms in infants

Infants		
Adverse Event	Intensity grade	Parameter
Fever*		Record temperature in °C/°F
	0	temperature <38.0°C/100.4° F
	1	temperature ≥38.0°C/100.4° F – ≤38.5°C/101.3 F
	2	temperature >38.5°C/101.3 F – ≤39.5°C/103.1 F
	3	temperature >39.5°C/103.1 F
Irritability/Fussiness	0	Behavior as usual
	1	Mild: Crying more than usual/no effect on normal activity
	2	Moderate: Crying more than usual/interferes with normal activity
	3	Severe: Crying that cannot be comforted/prevents normal activity
Diarrhea [§]		Record the number of looser than normal stools/day
	0	Normal (0-2 looser than normal stools/day)
	1	3 looser than normal stools/day
	2	4-5 looser than normal stools/day
	3	≥6 looser than normal stools/day
Vomiting [§]		Record the number of vomiting episodes/day
	0	Normal (no emesis)
	1	1 episode of vomiting/day
	2	2 episodes of vomiting/day
	3	≥3 episodes of vomiting/day
Loss of appetite	0	Appetite as usual
	1	Mild: Eating less than usual/no effect on normal activity
	2	Moderate: Eating less than usual/interferes with normal activity
	3	Severe: Not eating at all
Cough/runny nose	0	Normal
	1	Mild: Cough/runny nose which is easily tolerated
	2	Moderate: Cough/runny nose which interferes with daily activity
	3	Severe: Cough/runny nose which prevents daily activity

* Fever is defined as temperature ≥38.0°C/100.4°F. The preferred location for measuring temperature in this study will be the oral cavity, the axilla and the rectum.

§Diarrhea is defined as passage of three or more looser than normal stools within a day.

§ Vomiting is defined as one or more episodes of forceful emptying of partially digested stomach contents ≥1 hour after feeding within a day.

The intensity grade for diarrhea, vomiting and fever as shown in [Table 13](#) will be scored at GSK Biologicals.

The investigator will assess the maximum intensity that occurred over the duration of the event for all unsolicited AEs (including SAEs) recorded during the study. The assessment will be based on the investigator's clinical judgement.

The intensity should be assigned to one of the following categories:

- 1 (mild) = An AE which is easily tolerated by the subject, causing minimal discomfort and not interfering with everyday activities.
- 2 (moderate) = An AE which is sufficiently discomforting to interfere with normal everyday activities.
- 3 (severe) = An AE which prevents normal, everyday activities

(in a young child, such an AE would, for example, prevent attendance at a day-care center and would cause the parent(s)/LAR(s) to seek medical advice.)

An AE that is assessed as Grade 3 (severe) should not be confused with a SAE. Grade 3 is a category used for rating the intensity of an event; and both AEs and SAEs can be assessed as Grade 3. An event is defined as ‘serious’ when it meets one of the pre-defined outcomes as described in Section 8.1.2.

8.2.3.2.2. Assessment of causality

The investigator is obligated to assess the relationship between study vaccines and the occurrence of each AE/SAE using clinical judgement. In case of concomitant administration of multiple vaccines/products, if possible, the investigator should specify if the AE could be causally related to a specific vaccine/product administered (i.e., investigational, control/placebo or co-administered vaccine). When causal relationship to a specific vaccine(s) cannot be determined the investigator should indicate the AE to be related to all products.

Alternative plausible causes, such as natural history of the underlying diseases, concomitant therapy, other risk factors, and the temporal relationship of the event to the study vaccines will be considered and investigated. The investigator will also consult the IB and/or SmPC and/or Prescribing Information for marketed products to determine his/her assessment.

There may be situations when a SAE has occurred and the investigator has minimal information to include in the initial report to GSK Biologicals. However, it is very important that the investigator always makes an assessment of causality for every event prior to submission of the Expedited Adverse Events Report to GSK Biologicals. The investigator may change his/her opinion of causality in light of follow-up information and update the SAE information accordingly. The causality assessment is one of the criteria used when determining regulatory reporting requirements.

Causality of all AEs should be assessed by the investigator using the following question:

Is there a reasonable possibility that the AE may have been caused by the study vaccine?

- YES : There is a reasonable possibility that the study vaccines contributed to the AE.
- NO : There is no reasonable possibility that the AE is causally related to the administration of the study vaccines. There are other, more likely causes and administration of the study vaccines is not suspected to have contributed to the AE.

If an event meets the criteria to be determined as ‘serious’ (see Section 8.1.2), additional examinations/tests will be performed by the investigator in order to determine ALL possible contributing factors for each SAE.

Possible contributing factors include:

- Medical history.
- Other medication.
- Protocol required procedure.
- Other procedure not required by the protocol.
- Lack of efficacy of the vaccines, if applicable.
- Erroneous administration.
- Other cause (specify).

